10. Are on a stable dose, defined as listed here, if using these medications:
 - 10a. oral 5-ASA therapy: The prescribed dose has been stable for at least 2 weeks prior to the screening endoscopy.
 - 10b. oral corticosteroid therapy (prednisone ≤ 20 mg/day or equivalent, or budesonide extended release tablets 9 mg/day [budesonide MMX]): The prescribed dose has been stable for at least 2 weeks before the screening endoscopy.
 - 10c. AZA, 6-MP, and methotrexate: The prescribed dose has been stable for at least 8 weeks before the screening endoscopy.

Diagnostic Assessments

11. Have clinically acceptable central laboratory test results at screening (retesting is allowed for hematology and chemistry), as assessed by the investigator, including
 - 11a. hematology
 - absolute neutrophil count ≥ 1.5 times (x) $10^9/L$ ($\geq 1.5 \times 10^3/\mu L$ or ≥ 1.5 GI/L)
 - platelet count $\geq 100 \times 10^9/L$ ($\geq 100 \times 10^3/\mu L$ or ≥ 100 GI/L)
 - hemoglobin ≥ 8.5 g/dL (≥ 85 g/L) for males and > 8.0 g/dL (> 80 g/L) for females
 - lymphocyte count ≥ 500 cells/ μL ($> 0.50 \times 10^3/\mu L$ or > 0.50 GI/L), and
 - total white blood cell count $\geq 3.0 \times 10^9/L$ ($\geq 3.0 \times 10^3/\mu L$ or ≥ 3.0 GI/L)
 - 11b. chemistry
 - serum creatinine ≤ 1 times upper limit of normal (ULN)

- estimated glomerular filtration rate (eGFR) (Modification of Diet in Renal Disease [MDRD]) ≥ 60 mL/min/1.73 m²³⁶
- total bilirubin level (TBL) ≤ 1 times ULN
- alanine aminotransferase (ALT) and aspartate aminotransferase (AST) ≤ 1 times ULN
- alkaline phosphatase (ALP) ≤ 1 times ULN

Note: Patients with an established diagnosis of Gilbert's syndrome (requires source documentation showing unconjugated hyperbilirubinemia, with no evidence of hemolysis) can be included with bilirubin levels ≤ 3 times ULN.

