6.5. Concomitant Therapy

Participants should be instructed to consult authorized site personnel before taking any new medications or supplements during the study. Authorized site personnel should consult the sponsor's medical monitor if there are any questions about concomitant therapies during the study.

Recording of concomitant therapy

Any medication or vaccine (including over-the-counter, bowel preparations or prescription medicines, vitamins, and/or herbal supplements) that the participant is receiving at the time of enrollment or receives during the study must be recorded in the Concomitant Medication eCRF along with

- reason for use
- route of administration, and
- dates of administration, including start and end dates.

Dosage information including dose level and frequency may also be collected when applicable.

Allowed concomitant therapy

Participants are encouraged to maintain their usual medication regimens for concurrent conditions or diseases throughout the study treatment periods, unless those medications are specifically excluded (see [Appendix 7](#)). Participants taking permitted UC concomitant medications are to keep doses stable unless modifications are needed due to AEs, and are to follow the instructions regarding dose stabilization in [Appendix 8](#).

Administration of prohibited UC medications, approved or investigational, constitutes treatment failure. Use of such medications should not be withheld if, in the opinion of the investigator, failure to prescribe them would compromise participant safety. Participants who require a prohibited medication to treat their UC must be discontinued from study drug (Section [7.1.1](#)).

If a concomitant medication is needed to treat an AE or for appropriate medical management, the investigator should base decisions on the participant and clinical factors, considering prohibited medications. A participant who initiates a prohibited medication for a non-UC indication may either discontinue the study drug or discontinue the prohibited medication.

Vaccinations

See [Appendix 7](#) and [Appendix 8](#) for requirements on the timing of vaccinations.

Use of prohibited medications after discontinuation of study drug

At discretion of the investigator, medications listed in [Appendix 7](#) are allowed after a patient discontinues study drug and completes the ETV.

Rescue therapy

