This study does not include rescue therapy. Participants who are nonresponders at Week 12 will be assigned to the highest dose of LY3471851 (**CC1** µg), as described in Section 4.1. If these participants remain nonresponders at Week 26, they will be discontinued from study drug and enter post-treatment follow-up period (Section 7.1.1).

Corticosteroid tapering

Participants who enter the study on oral corticosteroid therapy for treatment of their UC should maintain the stable dose of corticosteroid during the entire 12-week induction period. Participants who achieve clinical response at Week 12 will initiate corticosteroid tapering, as described below. For participants who cannot tolerate the corticosteroid taper without recurrence of clinical symptoms, corticosteroid taper may be paused and/or corticosteroid dose may be increased up to the original dose at induction baseline (should not exceed induction baseline dose). In such cases, attempts to reinitiate corticosteroid tapering should be made within 2 weeks of interruption of taper, with a goal to complete tapering no later than Week 26.

Week 12 clinical nonresponders who undergo extended induction with the high dose of LY3471851 will begin corticosteroid tapering if clinical response is achieved at Week 26. For participants who cannot tolerate the corticosteroid taper without recurrence of clinical symptoms, corticosteroid taper may be paused and/or corticosteroid dose may be increased up to the original dose at induction baseline (should not exceed induction baseline dose). In such cases, attempts to reinitiate corticosteroid tapering should be made within 2 weeks of interruption of taper, with a goal to complete tapering no later than Week 40.

The recommended tapering schedule for oral corticosteroids (other than budesonide extended release tablets [budesonide MMX] or beclomethasone dipropionate [gastro-resistant prolonged release tablet]) is as follows.

Dose >10 mg/day prednisone or equivalent: taper daily dose by 5 mg/week until receiving 10 mg/day, and then continue tapering at 2.5 mg/week until 0 mg/day.

Dose ≤10 mg/day prednisone or equivalent: taper daily dose by 2.5 mg/week until 0 mg/day.

The recommended tapering schedule for participants receiving oral budesonide MMX 9 mg/day is to reduce tablets to 9 mg every other day for 2 weeks, followed by 9 mg every third day for 2 weeks, and then discontinue.

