- Participants who are discontinued from study drug because of a hepatic event or liver test abnormality should have additional hepatic safety data collected via the hepatic eCRF packet. Discontinuation of study drug because of abnormal liver tests should be considered by the investigator when a participant meets 1 of the following conditions after consultation with the sponsor's designated medical monitor (see Section 8.2.9):
 - ALT or AST >8 times ULN
 - ALT or AST >5 times ULN sustained for more than 2 weeks
 - ALT or AST >3 times ULN and TBL >2 times ULN or INR >1.5
 - ALT or AST >3 times ULN with the appearance of fatigue, nausea, vomiting, right upper quadrant pain or tenderness, fever, rash, and/or eosinophilia ($>5\%$)
 - ALP >3 times ULN
 - ALP >2.5 times ULN and TBL >2 times ULN, or

- ALP >2.5 times ULN with the appearance of fatigue, nausea, vomiting, right upper quadrant pain or tenderness, fever, rash, and/or eosinophilia (>5%).

Other reasons for permanent discontinuation of study drug

- The participant
 - scores a 3 for Item 12 (Thoughts of Death or Suicide) on the QIDS-SR16 at any time in the study, or
 - reports suicidal ideation or suicidal behaviors during the study.

Note: A psychiatrist or appropriately trained professional may assist in the decision to discontinue the participant from study drug.

- The participant requires treatment for exacerbation of UC and the treatment involves 1 or more medications at doses higher than those specified in the “dose stabilization” inclusion criterion; for example, the participant requires prednisone >20 mg/day) (see [Appendix 8](#)).
- The participant requires treatment with prohibited medications specified in the “prohibited medications” exclusion criterion, for example, a course of IV corticosteroids or a single dose of infliximab or IV cyclosporine (see [Appendix 7](#)).
- The participant was nonresponder at Week 12 and remains a treatment nonresponder at Week 26.

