9.4.1.2. Missing Data Imputation

While every effort will be made to minimize missing data, the missing data imputation methods described here will be used to provide a conservative approach for assessing efficacy endpoints when participants are permanently discontinued from study drug or otherwise have missing data.

- Nonresponder imputation (NRI): For analysis of categorical efficacy and health outcomes variables, missing data will be imputed using an NRI method. Participants will be considered nonresponders for the NRI analysis if they do not meet the categorical efficacy criteria or have missing clinical efficacy data at a time point of interest.
- The NRI method may be used when the estimand of interest uses the composite strategy³⁵ for handling intercurrent events. In this strategy, participants with any intercurrent events that lead to the permanent discontinuation of assigned study treatment are defined to have failed treatment for all subsequent timepoints.
- In addition, participants who were not adequately assessed to determine if they meet the clinical requirements for response at the time point of interest are also considered to have failed treatment.
- Mixed-effect Model for Repeated Measures (MMRM): For continuous variables, the primary analysis will be MMRM with the missing at random assumption for handling

missing data. This analysis takes into account both missingness of data and the correlation of the repeated measurements. No additional imputation methods will be applied to the MMRM analysis. The MMRM method may be justified when the estimand of interest uses the hypothetical strategy³⁵ for handling intercurrent events. In this strategy, the scientific question of interest is to assess the effect of study treatment in a hypothetical trial where all patients have complete data and continue to take study treatment without dropping out of the study or receiving rescue therapy.

For participants discontinuing study drug for any other reason, the last nonmissing postbaseline observation before discontinuation will be carried forward to the corresponding primary endpoint for evaluation.

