10.8. Appendix 8: Permitted Medications with Dose Stabilization

Drug Class	Dose Stabilization Guidance
Oral 5-ASAs for UC (for example, mesalamine, balsalazide, olsalazine and sulfasalazine)	The prescribed dose must have been stable for at least 2 weeks prior to the screening endoscopy, with stable dose encouraged during the study.
Oral corticosteroids for UC (prednisone \leq 20 mg/day or equivalent, budesonide MMX 9 mg/day, or beclomethasone dipropionate [gastro-resistant prolonged-release tablet] 5 mg/day)	Prescribed dose must have been stable for at least 2 weeks before screening endoscopy. See Section 6.5 for instructions on tapering of oral corticosteroid therapy.
Corticosteroids for non-UC indications: corticosteroids to treat adrenal insufficiency, or locally administered corticosteroids (for example, inhaled, intranasal, intra-articular, or topical)	May continue corticosteroids to treat adrenal insufficiency or locally administered corticosteroids during study with stable dose encouraged.
Immunomodulators (for example, AZA, 6-MP, or methotrexate)	Prescribed at stable dose for at least 8 weeks before screening endoscopy; doses should remain stable throughout study unless medication is discontinued due to a toxicity related to the medication.
Antidiarrheals (for example, loperamide or diphenoxylate with atropine)	May continue during study with stable doses encouraged.
Low-dose or baby aspirin (75 to 162.5 mg)	Daily use for cardiovascular prophylaxis permitted.
Non-live (killed, inactivated, or subunit) vaccines	Allowed during the study. The efficacy of non-live vaccinations with concomitant LY3471851 treatment is unknown.

Abbreviations: 5-ASA = 5-aminosalicylic acid; 6-MP = 6-mercaptopurine; AZA = azathioprine; UC = ulcerative colitis.

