4.3.2. Main analytical approach

The primary objective of this study is to test the hypothesis that treatment with LY3471851 is superior to placebo in inducing clinical remission at Week 12 in patients with moderate to severe ulcerative colitis (UC).

The rates of clinical remission and non-remission will be summarized by treatment group and by the stratification factors, previous advanced therapy failure status (yes/no), baseline corticosteroid use (yes/no), baseline disease activity (MMS: [4 to 6] or [7 to 9]), and region (North America/Europe/Other).

The primary analysis will use the CMH chi-square test to compare LY3471851 to placebo at Week 12. The stratification factors used for CMH test are (a) previous advanced therapy failure status (yes/no), (b) baseline corticosteroid use (yes/no), (c) baseline disease activity (MMS: [4 to 6] or [7 to 9]), and (d) region (North America/Europe/Other). See Section 4.1.1 for details on the methods to be used to test the differences between each active treatment arm and placebo.

Ninety five percent confidence interval along with the p-value for the difference in proportions (LY arm – placebo) for each pairwise comparison will be obtained. For a pairwise comparison, if p-value is less than 0.05, then that LY arm will be considered to be superior to placebo.

A composite strategy is proposed for other intercurrent events including discontinuing study intervention, taking prohibited medications or increase the dose of mandatory stable medications. The NRI methodology described in Section 4.1.2.1 will be applied when any of these events occur.

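### Starting a permitted oral corticosteroid, or starting or raising oral 5-ASA, before Week 12 is not clearly a nonresponse under the SAP, so remission due to background drugs could count in the primary endpoint

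*Protocol*

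**What the plan says.** **When study drug stops.** Protocol 7.1.1 requires permanent discontinuation when "The participant requires treatment for exacerbation of UC and the treatment involves 1 or more medications at doses higher than those specified" in the dose-stabilization inclusion criterion, "for example, the participant requires prednisone >20 mg/day", or when a prohibited drug is needed. Inclusion Criterion 10 caps oral corticosteroids (prednisone 20 mg/day, budesonide MMX 9 mg/day). For 5-ASA it asks only for stability: "oral 5-ASA therapy: The prescribed dose has been stable for at least 2 weeks prior to the screening endoscopy". It gives no dose for AZA, 6-MP or methotrexate either.

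**What may change during induction.** Protocol 6.5 tells participants on permitted UC drugs to hold their doses, with an exception for adverse events only. It adds that those entering on oral corticosteroids "should maintain the stable dose of corticosteroid during the entire 12-week induction period". For oral 5-ASA, Appendix 8 asks for a stable dose before the screening endoscopy, "with stable dose encouraged during the study". Protocol 7.2 lists a need for another effective UC agent among the circumstances in which a participant may withdraw, with study discontinuation before that agent is introduced.

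**What counts as failure.** Under protocol 9.4.1.2, "participants with any intercurrent events that lead to the permanent discontinuation of assigned study treatment are defined to have failed treatment"; inadequate assessment is also failure. SAP 4.3.2 applies nonresponder imputation to discontinuation and to "taking prohibited medications or increase the dose of mandatory stable medications". The SAP 1.1 primary estimand uses the same three conditions. It also names a change in background treatment as an intercurrent event.

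**What is recorded.** On concomitant drugs, protocol 6.5 says: "Dosage information including dose level and frequency may also be collected when applicable".

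**The concern.** Stool frequency, rectal bleeding and endoscopic appearance make up the whole primary endpoint. Oral corticosteroids and 5-ASA are UC treatments that can be expected to improve all three. If a participant who flares in induction can be treated with such a drug, stay on study drug and still be scored as a Week 12 remitter, the endpoint partly measures background treatment. Flares needing treatment are likely to be commoner on placebo (an expectation, not a figure in the documents), so spurious remissions would gather there and shrink the difference. With a planned placebo rate of only 5%, a few such cases matter.

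The recording rule adds to this. Detecting an increase requires dose and frequency data, and these are optional.

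**Working it through.** **Step 1. Apply the rules to each type of change before Week 12.** Each change is for UC and stays within the corticosteroid cap where one exists.

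| Change | Stops study drug under 7.1.1? | Failure under protocol 9.4.1.2? | Failure under SAP 4.3.2? |
|---|---|---|---|
| Corticosteroid already taken is raised (e.g. 5 to 20 mg/day) | No, not above the cap | No, unless study drug is stopped | Yes: 6.5 says the dose should be held through induction, so this is most naturally an increase of a mandatory stable drug |
| Oral corticosteroid newly started at or below the cap | No | No, unless study drug is stopped | Not named: permitted by Appendix 8, and a start is not plainly a dose increase |
| Oral 5-ASA started | No, no dose specified | No, unless study drug is stopped | Not named, for the same reason |
| Oral 5-ASA raised | No, no dose specified | No, unless study drug is stopped | Undecidable: 6.5 says hold the dose, Appendix 8 only encourages it |

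**Step 2. See whether other text closes the gap.**
- SAP 1.1 names a change in background treatment and classes data after rescue as nonresponse. The same estimand declares a composite strategy but labels its treatment condition as treatment policy. It sends the reader to Section 6 for rescue and concomitant interventions. SAP Section 6 has no such list, and protocol 6.5 says the study has no rescue therapy.
- SAP 4.1.2.1, the imputation section that 4.3.2 invokes, names only study discontinuation and inadequate assessment.
- Protocol 7.2 is permissive. If it covers permitted oral corticosteroids, it conflicts with the higher threshold in 7.1.1.

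**Step 3. Reproduce the plan's power.** Inputs from protocol 9.2: placebo 5%, active 35%, placebo n = 40, active n = 40, 60 or 80, alpha 0.05/3. With the arcsine formula and two-sided alpha:

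h = 2·arcsin√p1 − 2·arcsin√p0; power ≈ Φ( h / √(1/n1 + 1/n0) − z )

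For 35% v 5%, h = 0.815. At 40 v 40, 0.815/√(1/40 + 1/40) = 3.645. Subtracting z = 2.394 gives 1.251, so power is 89.5%. For 60 and 80 the results are 94.5% and 96.5%. All three stated figures are reproduced.

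**Step 4. Use the alpha of the planned test.** Protocol 9.4.1.3 and SAP 2.1 make no multiplicity adjustment, and SAP 4.3.2 tests each comparison at 0.05. With z = 1.960, the same formula gives 95% (40 v 40) and 99% (80 v 40).

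**Step 5. Illustrate the effect.** The documents give no rate of background-drug changes, so these inputs are assumptions. Let fp and fa be the proportions of placebo and active participants who start or raise such drugs, and r the share of them who remit only because of it. Then p0 = 0.05 + fp·r and p1 = 0.35 + fa·r.

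| fp, fa, r | p0 | p1 | Difference | 40 v 40 at 0.05 | 80 v 40 at 0.05 | 40 v 40 at 0.05/3 | 80 v 40 at 0.05/3 |
|---|---|---|---|---|---|---|---|
| none | 5% | 35% | 30 points | 95% | 99% | 89.5% | 96.5% |
| 10%, 5%, 20% | 7% | 36% | 29 points | 92% | 97% | 83% | 93% |
| 15%, 5%, 30% | 9.5% | 36.5% | 27 points | 85% | 93% | 73% | 86% |
| 25%, 10%, 40% | 15% | 39% | 24 points | 70% | 82% | 53% | 68% |

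The difference also shrinks if the same fraction of would-be non-remitters is converted in both arms. At 5% conversion the rates are 0.05 + 0.05 × 0.95 = 9.75% and 0.35 + 0.05 × 0.65 = 38.25%, a difference of 28.5 points.

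**The case against.** The strongest reply is that the documents already discourage these changes and largely handle them. Protocol 6.5 tells participants on permitted UC drugs to hold doses, with no exception for flares. Protocol 7.2 contemplates leaving the study before a new effective agent starts, and leaving before Week 12 is nonresponse. The reasons listed in 7.1.1 are not exhaustive, so an investigator may stop study drug. SAP 1.1 names background change as an intercurrent event. Protocol 9.4.1.1 defers the detail to the SAP, so 9.4.1.2 should not be read alone.

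Much of this stands. A reader might infer that raising prednisone within 20 mg/day also escapes the SAP. It does not: SAP 1.1 and 4.3.2, read with protocol 6.5, make it nonresponse. A reader might also infer that the protocol plainly permits escalation. It does not; its sections disagree.

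The gap remains all the same. The instructions to hold a dose address people already taking the drug. A breach is a deviation, and 6.5 does not make it an endpoint failure. Protocol 7.2 and the open list in 7.1.1 allow discontinuation but do not require it. The estimand's background-change event carries a contradictory label and has no operational definition.

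**Conclusion.** The point holds as a gap in the nonresponse rule. As written, SAP 4.3.2 does not catch a new start of a permitted oral corticosteroid or a start of oral 5-ASA before Week 12. Whether it catches a raised 5-ASA dose cannot be decided, because the mandatory stable medications are never defined. A raised corticosteroid dose is nonresponse under the SAP but not under protocol 9.4.1.2, although SAP Section 1 says the protocol's analyses are unchanged.

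The likely direction is towards no effect, on the assumption that flares are treated more often on placebo. The size is unknown. The 92% to 70% range for 40 v 40 (97% to 82% for 80 v 40) rests on assumed rates. Those rates also include corticosteroid increases that the SAP already scores as failures, so the uncaught part is smaller. The 53% figure uses the Bonferroni level of the sample-size section and should not be read as the loss for the planned test, which is unadjusted.

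**What to change.** 1. In SAP 1.1, 4.1.2.1 and 4.3.2, and in protocol 9.4.1.2, replace the reference to mandatory stable medications (or add, where it is absent) with an explicit scoring rule for the Week 12 endpoints. Any new start, or any increase above the participant's own baseline dose, of oral corticosteroid, oral 5-ASA, AZA, 6-MP or methotrexate for UC between baseline and the Week 12 assessment is scored as nonresponse. Delete the treatment policy label from the composite estimands.
2. Make dose and frequency required eCRF fields for these drug classes.
3. Reconcile protocol 6.5, 7.1.1, 7.2 and Appendix 8 on background-drug changes during induction. Which clinical rule applies is for the sponsor; the scoring rule in item 1 does not depend on that choice.

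The cost is wording in both documents and two more required fields for a short list of drugs. Observed remission rates will be slightly lower, because a few more participants are scored as nonresponders. The change should be made before the first unblinded interim analysis, since missing dose data are hard to recover later.

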7.1.2. Criteria for Temporary Interruption (Withholding) of Study Drug

7.1.2.1. Infection-Related Criteria for Temporary Interruption of Study Drug

Temporary withholding of study drug is required for the development of any of the following infection-related criteria during the study:

- Serious or opportunistic infections, as defined in Section 5.2. Study drug is to be withheld until resolution of all acute clinical signs and symptoms, and completion of all appropriate anti-infective treatment (exception for LTBI).
- Participants diagnosed with LTBI during the study are to be permanently discontinued from study drug unless the participant is a candidate for LTBI treatment, and is treated for LTBI as follows:
 - Study drug is temporarily withheld for at least the first 4 weeks of LTBI treatment.
 - After receiving at least 4 weeks of appropriate LTBI therapy (as per WHO and/or the United States Centers for Disease Control guidelines), if there is no evidence of hepatotoxicity (ALT/AST must remain ≤ 2 times ULN) or other treatment intolerance, study drug may be resumed.
 - The participant must complete appropriate LTBI therapy to remain eligible to receive study drug.
- HBV DNA results that are reported as positive, or as detecting HBV DNA, but HBV DNA is below the level of quantification. The sponsor's designated medical monitor should be contacted regarding study status of the participant. HBV DNA testing is to be repeated as soon as is feasible. If HBV DNA is confirmed as positive, the participant must be permanently discontinued from study drug (Section 7.1).

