7.1.1. Criteria for Permanent Discontinuation of Study Drug

Data collection and safety follow-up when study drug is permanently discontinued

In rare instances, it may be necessary for a participant to permanently discontinue (definitively discontinue) study intervention.

If study intervention is permanently discontinued, the participant will remain in the study to be evaluated at the ETV and post-treatment follow-up visits.

See the SoA for data to be collected at the time of discontinuation and follow-up and for any further evaluations that need to be completed. Safety follow-up is as outlined in the SoA, Section 8.2, and Section 8.3.

Criteria for permanent discontinuation of study drug

Possible reasons for permanent discontinuation of study drug include, but are not limited to, the following:

Participant decision

- The participant requests to discontinue the study drug.

Pregnancy

- The participant becomes pregnant during the study (see Section 8.2.5.1). Pregnant patients **will not** undergo an endoscopy at the ETV.

Safety considerations

- The participant develops any of the following conditions during the study:

- malignancy (except for successfully treated basal or squamous cell skin carcinoma)
 - dysplasia occurring in flat mucosa
 - dysplasia-associated lesion or mass (DALM)
 - HIV infection/acquired immune deficiency syndrome (AIDS)
 - active TB infection or untreated LTBI (Section 7.1.2; Section 8.2.6)
 - HCV RNA positive (Section 8.2.8)
 - HBV DNA positive and clinical assessment consistent with HBV reactivation
 - **Note:** The HBV DNA result is to be confirmed if initial positive test result is positive but below the level of quantification (Section 7.1.2; Section 8.2.7). The participant is to be referred to, evaluated, and managed by a specialist physician with expertise in evaluation and management of viral hepatitis prior to discontinuation of any immunomodulatory and/or immunosuppressive therapy, including study drug. Timing of discontinuation from study drug relative to the initiation of any antiviral treatment for hepatitis is to be based on the recommendation of the consulting specialist physician, in conjunction with the investigator, and aligned with medical guidelines and standard of care.
-
- The participant requires a colectomy, proctocolectomy, or partial colectomy during the study.

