8.2.7. Hepatitis B Testing and Monitoring

Initial testing for HBV infection includes hepatitis B surface antigen (HBsAg) and antibody to hepatitis B core antigen (anti-HBc).

- If HBsAg is positive, the participant is excluded.
- If HBsAg is negative and anti-HBc is negative, the participant is not excluded.
- If HBsAg is negative and anti-HBc is positive, further testing for HBV DNA is required.
 - If the screening HBV DNA is positive, the participant is excluded.
 - If the screening HBV DNA is negative, the participant is not excluded. Repeat testing for HBV DNA is required at least approximately every 8 to 14 weeks during the study (see the timing in the SoA), with temporary withholding or permanent discontinuation of study intervention if HBV DNA is positive, as described in Section 7.

Management of enrolled participants with detectable HBV DNA during the study

If HBV DNA is detected during the study, the study drug will be temporarily withheld or discontinued and participants should receive appropriate follow-up medical care as described in Section 7.

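### Protocol Sections 7.1.1 and 7.1.2.1 give inconsistent triggers for permanently stopping study drug after a positive HBV DNA result, and neither covers a quantifiable result without clinical signs

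*Protocol*

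**What the plan says.** Participants who are HBsAg-negative, anti-HBc-positive and HBV DNA-negative at screening may enter the study and have repeat HBV DNA tests (Protocol Section 8.2.7). Three places say what follows a positive on-study result.

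- **Section 7.1.1 (permanent discontinuation).** The listed condition is "HBV DNA positive and clinical assessment consistent with HBV reactivation". A note adds "The HBV DNA result is to be confirmed if initial positive test result is positive but below the level of quantification" and refers to Sections 7.1.2 and 8.2.7. It requires referral to, and evaluation and management by, a viral hepatitis specialist before study drug is stopped. It also says "Timing of discontinuation from study drug relative to the initiation of any antiviral treatment for hepatitis is to be based on the recommendation" of that specialist, acting with the investigator.
- **Section 7.1.2.1 (temporary interruption).** The bullet covers "HBV DNA results that are reported as positive, or as detecting HBV DNA, but HBV DNA is below the level of quantification". The medical monitor should be contacted and the test repeated. Then: "If HBV DNA is confirmed as positive, the participant must be permanently discontinued from study drug". The sentence cites Section 7.1.
- **Section 8.2.7 (monitoring).** The plan is repeat testing "with temporary withholding or permanent discontinuation of study intervention if HBV DNA is positive, as described in Section 7". The management paragraph says "If HBV DNA is detected during the study, the study drug will be temporarily withheld or discontinued" and again refers to Section 7.

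**The concern.** Section 7.1.1 joins two conditions, a positive result and a clinical assessment. Section 7.1.2.1 makes the stop mandatory on the laboratory result alone. It cites Section 7.1 as its authority, yet the only HBV DNA criterion there, in 7.1.1, is the two-part one. Section 8.2.7 sends the reader back to Section 7 and so cannot settle the matter.

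At stake is uniform handling of a foreseeable safety event. Two sites could treat the same result differently, and the procedures around it differ too: 7.1.1 brings in a specialist before the stop, while 7.1.2.1 names only the medical monitor.

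There is also a consequence for the analysis. Under the composite strategy (Protocol Section 9.4.1.2; SAP Section 4.3.2), permanent discontinuation makes a participant a treatment failure. Temporary withholding is not listed as a failure event.

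**Working it through.** No arithmetic applies. The check applies each rule to the four possible cases and then reads the HBV DNA testing schedule.

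**Step 1: the cases.** SAP Section 4.6.3.1 itself separates detectable but not quantifiable (below 29 IU/mL) from quantifiable (29 IU/mL or more), so the split is one the plan already uses.

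| HBV DNA result | Clinical assessment | Section 7.1.1 criterion | Section 7.1.2.1 rule | Outcome |
|---|---|---|---|---|
| Below quantification, confirmed | Consistent with reactivation | Met | Permanent stop required | Agree |
| Below quantification, confirmed | Not consistent | Not met | Permanent stop required | **Conflict** |
| Quantifiable | Consistent with reactivation | Met | Does not apply | 7.1.1 alone |
| Quantifiable | Not consistent | Not met | Does not apply | **Gap**: only Section 8.2.7, which allows either action |

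Read literally, the mandatory stop attaches to a confirmed low-level result, while a quantifiable result with the same clinical picture has no definite HBV-specific rule.

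**Step 2: when a result can arise.** Scheduled HBV DNA tests, for anti-HBc-positive participants only (Protocol Section 1.3, Tables 1 to 4):

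- all such participants: screening (V1) and Week 12 (V9);
- Week 12 Responders: Weeks 24, 36 and 48;
- Week 12 Nonresponders: Weeks 26, 38 and 48;
- also at the early termination visit and at V802.

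**Step 3: which endpoints are exposed.** The first scheduled on-treatment sample is taken at the primary-endpoint visit itself. Its result, any repeat test and any decision to stop come afterwards, and Protocol Section 9.4.1.2 counts failure for time points after the event. A stop before Week 12 would need an unscheduled test, for instance in the hepatic work-up of Section 8.2.9, for which Appendix 5 lists HBV DNA. The exposed efficacy endpoints are therefore mainly the Week 52 responder endpoints among Week 12 Responders. There, a permanent stop fixes the participant as a failure, and a withheld participant may still qualify.

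**The case against.** The strongest reply is that a site can obey both sections. The list in 7.1.1 opens with "Possible reasons for permanent discontinuation of study drug include, but are not limited to, the following", so its HBV item is one reason to stop and does not oblige anyone to continue. The mandatory wording of 7.1.2.1 could then govern a confirmed low-level result. The 7.1.1 note also cross-refers to 7.1.2 and 8.2.7, and specialist referral and contact with the medical monitor make unsupervised divergence less likely.

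Much of this stands, and it limits the point in two ways.

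- A reader might infer that one section would keep such a participant on treatment. The documents do not support that. No section directs continued dosing on a detected result, and 8.2.7 requires drug to be withheld or discontinued. The divergence is between withholding and a permanent stop.
- A reader might also infer that one event could be scored two ways on the primary endpoint. The composite rule is single and follows what actually happened to treatment, so variation would come from conduct. The testing schedule also leaves Week 12 remission largely out of reach.

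The reply does not remove the inconsistency. The site has to construct that reading, and it leaves the clinical-assessment condition without effect for confirmed low-level results. It does nothing for the quantifiable case. There, the general grounds in 7.1.1 (investigator's opinion on a laboratory change) and 7.1.2.2 (abnormal values of unclear relationship to drug) permit action but do not fix it. Case-by-case advice does not make the written rules agree, and 7.1.2.1 leaves no discretion once the result is confirmed.

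**Conclusion.** The inconsistency is real and narrow. One class of participant (confirmed low-level result, no clinical signs) meets one criterion and not the other. A second class (quantifiable result, no clinical signs) meets neither. Only participants anti-HBc-positive at screening have scheduled tests. Their number is not given, and the point does not depend on it. The effect is on patient safety, consistency between sites and Week 52 failure status; the effect on the primary analysis is small.

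This rests on two readings. First, the below-quantification limit in 7.1.2.1 is taken to apply to the whole bullet. If it qualified only results described as detecting HBV DNA, the gap would close, but the conflict with 7.1.1 would extend to quantifiable results. Second, a clinical assessment consistent with reactivation is taken to require more than the laboratory result. If the sponsor means a confirmed positive to satisfy it, the protocol should say so. Either way the text needs clarifying. No view is offered on which clinical rule is right.

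**What to change.** Reconcile Sections 7.1.1 and 7.1.2.1 so that one trigger for permanent discontinuation applies and is stated for both below-quantification and quantifiable results, with and without clinical signs. State in the same place whether the specialist evaluation and timing provisions of the 7.1.1 note apply to a stop made under 7.1.2.1. Section 8.2.7 can go on cross-referring to Section 7 and need not repeat the criterion. The choice of trigger belongs to the sponsor's medical team.

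The cost is a protocol clarification and notice to sites. The estimand and analysis need no change, because the composite rule already follows the actual treatment decision.
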